5.2.3 Secondary Effectiveness Endpoints

The secondary effectiveness endpoints will include:

- Δ CAL from baseline at three months and Δ CAL at three and six months post-implantation
 - CAL is theoretically calculated by addition of PD and GR. The mean change in CAL is compared to a historically established level (1.5 mm) of clinical effectiveness at three months post-implantation, and the mean Δ CAL between study treatments are compared at three and six months post-implantation;
- LBG at six months post-implantation;
- Percent bone fill (%BF) at six months post-implantation;
- Composite endpoint combining Δ CAL and %BF at six months post-surgery - The success criteria are a minimum of 1.5 mm for Δ CAL and a minimum of 10% for %BF. Both the Δ CAL and %BF must meet the success criteria for a subject to be considered a success;

- Probing Depth Reduction (PDR) from baseline at three and six months post-implantation - PDR is the difference between the PD (pocket depth) at baseline, three months and six months. PD is the distance from the gingival margin generally along the long axis of the tooth to the deepest extent of the periodontal pocket;
- Change in Gingival Recession (Δ GR) from baseline at three and six months post-implantation - GR at three and six months post-implantation: GR is the distance from the free gingival margin to the CEJ;
- Wound-Healing (WH) scale two and four weeks post-implantation - A wound-healing scale modified from the index described by Lobene *et al.* (1986)⁽⁷⁾ will be used to assess wound healing during the first four weeks post-implantation. The assessment will be made of the gingival tissues superficial to the grafted osseous defect using the scale is shown below:
 - 0 = Absence of inflammation, normal healthy appearance to the tissues superficial to the graft;
 - 1 = Mild inflammation, slight marginal change in color (e.g. redness), little change in texture of any portion of the marginal or papillary gingival unit superficial to the graft;
 - 2 = Mild inflammation; criteria as above but involving the entire marginal or papillary gingival unit;
 - 3 = Moderate inflammation; glazing, redness, edema, and/or hypertrophy of the marginal or papillary unit, bleeding on gentle palpation; and
 - 4 = Severe inflammation; marked redness, edema, and/or hypertrophy of the marginal or papillary gingival unit, spontaneous bleeding, congestion.

- Gingival wound evaluation – evaluated as closed, open <2 mm or open ≥ 2 mm at two and four weeks post-implantation;
- Bleeding on probing (BOP) at three months post-implantation - Presence or absence of bleeding on probing at each site, recorded 10 seconds after probing of the particular quadrant.

All secondary endpoints will be evaluated by treatment group.

Δ CAL at three and six months, and LBG and %BF at six months were set as secondary endpoints to evaluate the effectiveness over time of the investigational product on both new connective tissue attachment and bone regeneration, respectively. BOP will be assessed to evaluate the effect of the investigational product on periodontal tissue inflammation. PD and GR will be assessed to evaluate tissue levels. WH scale and gingival wound evaluation will be assessed to evaluate the effect of the investigational device on the wound healing process.

Standardized radiographs will be obtained at baseline and three and six months post-implantation. These radiographs will be analyzed for bone growth as well as adverse events.

5.2.4 Safety Endpoints

Safety will be monitored throughout the study by assessing the incidence, timing, and severity of Adverse Events. Adverse events with clinical signs or symptoms will be collected when volunteered by subjects and/or observed by Investigators. Additionally, blood serum collected at two and four weeks post-implantation will be analyzed for antibody formation against rh-bFGF. Subjects with increase of specific antibody production against rh-bFGF will have blood serum collected at subsequent follow-up visits for testing until their results return to baseline values. If a subject is diagnosed with a precancerous lesion such as leukoplakia after the study starts, it will be biopsied as appropriate for further analyses. Also, radiographs obtained at three and six months post-implantation will be reviewed and compared to baseline to detect adverse events such as ankylosis, root resorption or other abnormal events in the bony architecture at the site.

5.3 Premature Termination or Suspension of Study or Investigational Site

5.3.1 Criteria for Premature Termination or Suspension of the Study

The study will be completed as planned unless one or more of the following criteria are satisfied and require temporary suspension or early termination of the study.

1. New information or other evaluation regarding the safety or effectiveness of the device that indicates a change in the known risk/benefit profile for the device, such that the risk/benefit is no longer acceptable for subjects participating in the study.
2. Significant violation of Good Clinical Practice (GCP) that compromises the ability to achieve the primary study objectives or compromises subject safety.
3. Sponsor decides to terminate the study.

5.3.2 Criteria for Premature Termination or Suspension of Investigational Sites

An investigational site may be terminated prematurely or suspended if the site (including the Investigator) is found in significant violation of GCP, the protocol, or the contractual agreement, is unable to ensure adequate performance of the study, or as otherwise permitted by the contractual agreement.

5.3.3 Procedures for Premature Termination or Suspension of the Study or the Participation of Investigational Site(s)

In the event that the Sponsor, an institutional review board (IRB) or regulatory authority elects to terminate or suspend the study or the participation of an investigational site, a study-specific procedure for early termination or suspension will be provided by the Sponsor; the procedure will

CONFIDENTIAL

be followed by applicable investigational sites during the course of termination or study suspension.

CONFIDENTIAL

6.0 SELECTION AND DISCONTINUATION/WITHDRAWAL OF SUBJECTS

6.1 Inclusion Criteria

Subjects must meet all of the following criteria to be entered into the study:

1. Male or female, age of 25 and older
2. Must have read, understood, and signed a consent form
3. Must be able and willing to follow study procedures and instructions
4. Must have undergone thorough scaling and root planing of the target tooth and be expected to demonstrate good plaque control after instruction in oral hygiene
5. The target tooth must exhibit the following:
 - A pocket depth of 7 mm or greater
 - After surgical debridement, 4 mm or greater intrabony defect with at least 1 bony wall
 - Sufficient keratinized tissue to allow complete tissue coverage of the defect
 - Radiographic base of defect at least 3 mm coronal to the apex of the tooth

6.2 Exclusion Criteria

1. Failure to maintain adequate oral hygiene during the screening phase
2. Women of child-bearing potential
3. A history within the last 6 months of HIV, Type IV heart disease, or end-stage renal disease
4. A history of oral cancer or any other cancer (exception: subjects with a history of skin cancers such as squamous and basal carcinoma with end of treatment at least 6 months ago and/or prostate cancer with end of treatment at least 5 years ago may be enrolled)
5. A history within 12 months of previous open flap periodontal surgery on the study tooth.
6. A diagnosis of pre-malignant oral lesion(s)
7. A traumatic occlusion of the target tooth
8. Target "study" tooth exhibiting Grade III mobility
9. Maxillary molars or maxillary first premolar with a prominent mesial concavity
10. Study tooth exhibiting a Class II or greater furcation defect
11. Clinical or radiographic signs of untreated acute or chronic periapical infection at the surgical site, apical pathology, root fracture, severe root irregularities, cemental pearls, cervical enamel projections not easily removed by odontoplasty, untreated carious lesions at the cemento-enamel junction (CEJ) or on the root surface, or restorations with open or otherwise defective margins at or below the CEJ
12. A history within the last 6 months of the daily use of any tobacco products besides cigarettes (smokeless chewing tobacco, pipe or cigar smoking), or of smoking more than 10 cigarettes per

day

13. Subjects participating in other clinical trials within 30 days of enrollment
14. Subjects having uncontrolled endocrine-induced diseases (e.g. uncontrolled diabetes mellitus and hyperparathyroidism)
15. Subjects undergoing current therapy with systemic steroids or other drugs that significantly alter bone metabolism
16. Subjects with Localized Juvenile Periodontitis (LJP) sites in the oral cavity

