treatment of periodontal intrabony defects and to help guide the selection of dosing for future study.

Subject Population: Subjects 25 years and older with advanced periodontal disease in at least one site requiring surgical treatment to correct a bone defect. A total of 94 subjects will be randomized to obtain a minimum of 80 evaluable subjects for this multicenter trial.

| Number of Subjects: | Number of investigational sites: |
|-----------------------|----------------------------------|
| 80 evaluable subjects | 6 sites |

Main Criteria for Inclusion:

Inclusion criteria include:

1. Male or female, age of 25 and older
2. Must have read, understood, and signed a consent form
3. Must be able and willing to follow study procedures and instructions
4. Must have undergone thorough scaling and root planing of the test site and be expected to demonstrate good plaque control after instruction in oral hygiene
5. The treated site must exhibit the following:
 - A pocket depth of 7 mm or greater
 - After surgical debridement, 4 mm or greater intrabony defect with at least 1 bony wall
 - Sufficient keratinized tissue to allow complete tissue coverage of the defect
 - Radiographic base of defect at least 3 mm coronal to the apex of the tooth

Main Criteria for Exclusion:

Significant exclusionary criteria are:

1. Failure to maintain adequate oral hygiene during the screening phase
2. Women of child-bearing potential
3. A history within the last 6 months of HIV, Type IV heart disease, or end-stage renal disease
4. A history of oral cancer or any other cancer (except for end of treatment for skin cancers such as squamous and basal carcinoma with end of treatment at least 6 months ago and/or prostate cancer with end of treatment at least 5 years ago)
5. A history within 12 months of previous open flap periodontal surgery on the study tooth
6. A diagnosis of pre-malignant oral lesion(s)
7. A traumatic occlusion of the target tooth
8. Target "study" tooth exhibiting Grade III mobility
9. Maxillary molars or maxillary first premolar with a prominent mesial concavity
10. Study tooth exhibiting a Class II or greater furcation defect

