3.5.3 Potential Risks Associated With rh-bFGF in GFeBGS

The rh-bFGF based product has been approved for treatment of dermal ulcers by the Japanese authority and in clinically used since 2001 with minimal adverse events reported in the post marketing surveillance report to the Pharmaceuticals and Medical Devices Agency for 8 years. Most of the adverse events were related to the skin and subcutaneous tissue and the administration site. There were rare reports of malignant tumors in the follow-up period whose causal relationship with the product could not be denied due to insufficient information. The safety and toxicological testing on rh-bFGF includes single dose toxicity, repeating dose toxicity, reproductive development toxicity, genetic toxicity (mutagenicity), local irritation, antigenicity, pyrogen test, skin carcinogenesis initiation, skin carcinogenesis promotion, effects on human tumor cells, effects on mouse melanoma cells, evaluation using a two-step model of hepatocarcinogenesis, *in vitro* transform study. No adverse events were observed throughout this series of studies. In summary, the safety, toxicity and biocompatibility data suggest that an rh-bFGF-based product is sufficiently safe for conducting a human clinical trial.

CONFIDENTIAL

However, the risk of promotion of cancer in a remote location cannot be denied because rh-bFGF has a promotional effect to accelerate a proliferation of various kinds of cells including several human tumor cell lines. Even though the probability of this risk is very low, its severity is considerable if it were to occur. To minimize the cancer promotion risk, the subjects with a history of oral cancer or having any other history of cancer (except for prostatic and skin cancer more than 5 years after treatment and skin cancer) are excluded in this study. If precancerous conditions of the mucous membrane are found in the oral cavity, it will be thoroughly examined and diagnosed before enrollment of the patient in this study. If the Investigator is unable to make a definitive diagnosis of the oral lesion, the Investigator will consult with an oral pathologist or a qualified specialist. Also, Investigators will be well trained about the proper preparation and use of GFeBGS before initiation of the study.

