8.3.1 Visit 1: Screening

After the Informed Consent for Screening is signed and a screening number is assigned, the screening assessment will be performed. It includes an oral, medical (including a complete record of current medications) and demographic history, smoking history and identification of one or more target teeth and bone defect(s). Note that only one tooth per subject may receive treatment

with the investigational product. However, the final study eligibility of a tooth cannot be determined until the surgery is underway. Therefore, identification of additional target teeth increases the likelihood that the subject will not be excluded from the study during surgery.

A periapical radiograph may be taken as necessary to ensure that all target teeth meet the inclusion and exclusion criteria (see Sections 6.1 and 6.2). If the subject satisfies all inclusion and exclusion criteria, one or more target teeth that meet the eligibility criteria will be identified. To be included in the study, a subject must undergo thorough scaling and planing of all teeth in the target tooth's quadrant within 2 months prior to the surgical procedure. If more than one target tooth is selected in more than one quadrant, each quadrant with a target tooth will undergo scaling and planing. Note that scaling and planing will be performed in other quadrants as necessary to treat disease. If scaling and planing are necessary, it should be performed at least two weeks prior to the Baseline Visit (Visit 4). If tissue inflammation caused by the pre-surgical treatment is observed at the Baseline Visit (Visit 4), the Baseline Visit should be postponed until the inflammation subsides.

A summary of all procedures to be performed is listed below.

Summary of Procedures/Measurements:

- Informed consent for screening must be obtained according to the process described in Section 14.2
- Complete Screening Assessment (CRF 1) and Pre-enrollment Eligibility and Assignment (CRF 2) forms
- Identify a single or, if possible, multiple target teeth
- Determine initial subject eligibility
 - If not eligible, subject is a screen failure and should be documented on the Screening Failure Log
 - If eligible, continue the visit
- Determine if 1 or 2 scaling and planing procedures and/or sustained oral hygiene instructions are necessary
 - If yes, schedule the procedure(s)
 - If no, Visit 4 (Baseline) may be conducted at the end of this visit
- If necessary:
 - Perform supragingival prophylaxis

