13.0 QUALITY CONTROL AND QUALITY ASSURANCE

13.1 Investigational Site Monitoring Visits

Each investigational site will be monitored on site, to ensure that the study is conducted in full compliance with the study protocol and in compliance with the FDA Guidelines for the Monitoring of Clinical Investigations (February,1988), Good Clinical Practices and Sunstar policies and procedures.

[REDACTED] will conduct regular clinical monitoring visits to each investigational site. Before beginning data collection for a given site, the site and personnel to be involved in the study at that site will be visited. The objectives of this pre-study visit are:

- to confirm that the Investigator and study personnel fully understand the Clinical Investigation Plan, the data collection procedures and the requirements to be met before starting the study;
- to confirm that the Investigator and study personnel fully understand the procedures related to the selection of study subjects for this study; and
- to confirm that the Investigator and study personnel have appropriate knowledge, experience and equipment to comply with the study requirements. Observations made during a pre-study visit will be documented by means of a pre-study monitoring report.

To ensure that the Investigators and their staffs understand and accept their defined responsibilities, the Clinical Monitor will maintain regular correspondence and perform periodic site visits during the course of the study to verify the continued acceptability of the facilities, compliance with the Investigational Plan, conditions of the IRB and requirements of the IDE regulations, complete documentation and reporting of any complications and Unanticipated Adverse Device Effects, and the maintenance of complete records. Clinical monitoring will include review and resolution of missing or inconsistent results, source document checks (i.e., comparison of submitted study results to original reports) to assure the accuracy of the reported data, review of the device inventory log and review of the investigational device storage conditions. The Clinical Monitor will also conduct a site close out visit. The Clinical Monitor will evaluate and summarize the results of each site visit in written reports, identifying any repeated data problems with the Investigator and specifying recommendations for resolution of noted deficiencies.

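### Exclusion criterion 4 exempts treated skin cancer by example and does not close the class; Section 3.5.3, which gives the reason for the exclusion, settles neither the type nor the interval

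*Protocol*

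**What the plan says.** Criterion 4 in Section 6.2 excludes anyone who has had oral cancer or any other cancer, with no time limit. It then makes two exceptions: "subjects with a history of skin cancers such as squamous and basal carcinoma with end of treatment at least 6 months ago", and prostate cancer whose treatment ended at least 5 years ago. The study summary (Section 1.0) has the same skin exception: "skin cancers such as squamous and basal carcinoma with end of treatment at least 6 months ago".

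Section 3.5.3 explains why the exclusion exists: "To minimize the cancer promotion risk, the subjects with a history of oral cancer or having any other history of cancer" are kept out. It puts the exceptions in a parenthesis: "except for prostatic and skin cancer more than 5 years after treatment and skin cancer". On the risk itself it says: "Even though the probability of this risk is very low, its severity is considerable if it were to occur". It also mentions, from experience with the marketed dermal product, "rare reports of malignant tumors in the follow-up period whose causal relationship with the product could not be denied due to insufficient information".

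Eligibility is judged at screening. Section 8.3.1 sends the site to Sections 6.1 and 6.2 and lists "Complete Screening Assessment (CRF 1) and Pre-enrollment Eligibility and Assignment (CRF 2) forms" among the tasks. The pre-study monitoring visit in Section 13.1 is meant "to confirm that the Investigator and study personnel fully understand the procedures related to the selection of study subjects for this study".

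**The concern.** The words *such as* introduce examples. They do not say that the two carcinomas are the only skin cancers exempted, and nothing else in 6.2 excludes the rest: criterion 6 concerns pre-malignant oral lesions, and the other criteria do not deal with cancer. A site that applies the sentence as written could enrol a subject treated for melanoma of the skin 6 months earlier and would be within the protocol.

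This matters because 3.5.3 names the exclusion as the measure against cancer promotion at a site remote from the graft, on the ground that rh-bFGF speeds proliferation of several human tumor cell lines. A safeguard of that kind should say exactly which cancers it lets through. The rationale gives no reason to exempt an unnamed skin cancer while most other cancers are barred for life.

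Later steps would not reliably catch such a case. Section 13.2 allows no exemptions from the criteria and asks for consultation when a deviation is needed, but enrolling under the literal text is not a deviation. The specialist consultation in 3.5.3 is for oral lesions that the investigator cannot diagnose. Routine adverse event collection stops at the final visit, 6 months after surgery (9.2.1.1). Much of the protection therefore rests on the wording of the criterion.

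**Working it through.** The plan states no figure on this point, so the check is a comparison of the texts.

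**Step 1. The three statements of the exception**

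| Section | Skin cancer types exempted | Time since skin cancer treatment | Time since prostate cancer treatment |
|---|---|---|---|
| 6.2, criterion 4 | open class, two carcinomas as examples | at least 6 months | at least 5 years |
| 1.0, criterion 4 | same open class | at least 6 months | at least 5 years |
| 3.5.3, parenthesis | no type given | more than 5 years, then named again with no interval | more than 5 years |

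Sections 6.2 and 1.0 agree with each other. Section 3.5.3 differs from both on the skin interval, and within itself.

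**Step 2. Apply each reading to two subjects whose treatment ended between 6 months and 5 years ago**

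| Reading | Basal cell carcinoma | Melanoma of the skin |
|---|---|---|
| 6.2 and 1.0, literal | eligible | eligible |
| 6.2 and 1.0, narrow (only the two named types) | eligible | excluded |
| 3.5.3, mention at more than 5 years | excluded | excluded |
| 3.5.3, mention with no interval | eligible | eligible |

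**Step 3. What follows**

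- Only the narrow reading of 6.2 separates the two subjects, and the protocol text nowhere states it.
- Neither mention in 3.5.3 separates them, because that section gives no type. The section a reader would consult for the intent therefore cannot support the narrow reading.
- Neither mention in 3.5.3 gives 6 months, so it cannot confirm the operative interval either.

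**Step 4. Size**

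The document gives no frequency of earlier skin cancer of any type among candidates. An expected number among the 94 randomized would need an assumed prevalence and an assumed share of sites reading literally. Neither has a basis in the text, so none is computed.

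**The case against.** The strongest reply is that the operative rule is consistent and its intent is plain. Sections 6.2 and 1.0 agree, and 8.3.1 sends sites to 6.1 and 6.2, not to the risk narrative in 3.5.3. The default is exclusion of every cancer, and an exception illustrated by two carcinomas with a short interval reads most naturally as covering that kind of lesion only. The parenthesis in 3.5.3 looks like an editing leftover. The case report forms and consent forms are not shown and might close the list. No harm from this class is shown: 3.5.3 lists a test on mouse melanoma cells within a series in which no adverse events were observed.

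Most of this stands, and it limits the weight of the point. It does not remove it. A natural reading is still not the written one, and for a safety exclusion the protocol itself should carry the definition.

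A reader might infer three stronger things that the documents do not support:

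- **That the sponsor means to admit melanoma.** No section names it as admitted, and the narrow reading is the more likely intent.
- **That the gap between the two intervals in 6.2 is itself a fault** (5 years is 60 months; 60 - 6 = 54 months). Different intervals for different cancers are a clinical choice, and the fix below keeps both.
- **That 3.5.3 sets a rival rule of 5 years for skin cancer.** It names skin cancer twice with different conditions, in a background section. It is a garbled sentence that fails to clarify the criterion, not a second criterion.

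**Conclusion.** The point holds as a wording defect in a safety criterion. The exempt class in criterion 4 is open, its literal reading admits any treated skin cancer at 6 months, and 3.5.3 settles neither the class nor the interval. The conclusion rests only on the visible protocol text; whether the unseen forms define the class is unknown.

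The size is minor to moderate. The protocol calls the underlying risk very unlikely but serious, the sponsor probably intended the narrow class, and few subjects are likely to be affected. Nobody should infer from this that an appreciable number of such subjects would be enrolled, because the document offers no figure from which to say so. The power assessment, the randomization, the endpoints and the analysis do not depend on it.

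**What to change.** Before screening starts, close the list in criterion 4 in both 6.2 and 1.0, for example:

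*Any history of cancer, oral or other. The only exceptions are (a) basal cell or squamous cell carcinoma of the skin, if treatment ended 6 months ago or longer, and (b) prostate cancer, if treatment ended 5 years ago or longer; a subject may have both. All other cancers, including melanoma, exclude the subject.*

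Replace the parenthesis in 3.5.3 with the same types and intervals, so that skin cancer appears once and with its interval. If the sponsor does mean to admit other skin cancers, it should name each with its own interval and give the reason in 3.5.3. CRF 1 and CRF 2 should be checked for agreement with the new wording.

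The cost is a text change in three places and possibly the loss of very few candidates. That loss falls at screening, before randomization, so the targets of 94 randomized and 80 evaluable subjects stay as they are.
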